## 1.2 Study population

All available data will be used for longitudinal and pairwise comparisons.

## 1.3 Statistics

### 1.3.1 Sample Size

The minimum clinically important change/difference in HUI3 is 0.03 units and in SSQ the minimum clinically important change/difference is 2 units. For HUI3 this change is very small and larger differences are typically observed. As such for these analyses we are interested in differences/changes of at least 0.1 units.

Calculating sample sizes for longitudinal designs is complicated and requires more assumptions that are difficult to ascertain than simpler designs. For these sample size calculations, we use a simple approach understanding that longitudinal designs are often more efficient and hence requiring smaller sample sizes than those we might estimate below.

#### Estimating the SD

For the sample size calculations, we require estimated standard deviations (SD) which are taken as follows:

HUI3: From Figure 9E pp326 of the UK Cochlear Implant Study Group (UKCISG) paper in Ear and Hearing (2004, Vol 25, Issue 4, pp310-315) we can calculate the SD for each age group from  $SD = \sqrt{N} * \frac{(\text{upper CI} - \text{lower CI})}{3.92}$  and then pool all of the SDs:

**Table 1: Estimates from Figure 9E of UKCISG paper**

Age group	20	30	40	50	60	70
N	39	35	59	75	70	33
Mean	0.24	0.22	0.21	0.16	0.20	0.18
SE=(upper-lower)/3.92	0.031	0.036	0.026	0.026	0.026	0.046
SD=SE*SQRT(N)	0.191	0.211	0.196	0.221	0.213	0.264
P-value for change in each age group	<0.001	<0.001	<0.001	<0.001	<0.001	<0.001

Then the pooled standard deviation for the difference between groups is equal to **0.22**. The mean change varies between 0.16 and 0.24 with smaller mean changes observed in older groups. There is a significant change (paired t-test) over time in each age group.

From Cochlear data HUI3 and SSQ category data are available pre and post-surgery for a sample of subjects though not by age group. Summaries are as follows:

**Table 2: Estimates of the mean and standard deviation from a sample of participants**

Outcome measure	HUI3 pre	HUI3 post	Diff (Paired)	Spatial pre	Spatial post	Spatial diff
N	29	38	27	47	49	38
Mean	0.53	0.65	0.09	3.55	4.60	1.18
SD	0.188	0.168	0.182	1.907	2.104	1.356
P-value			0.016			<0.001
Outcome measure	Speech pre	Speech post	Speech diff	Qual pre	Qual post	Qual diff
N	49	51	40	52	50	40
Mean	4.53	5.62	1.18	2.85	4.65	1.80
SD	1.707	1.685	1.919	1.355	1.726	1.289
			<0.001			<0.001

For SSQ the SD for change varies between 1.3 and 1.9. A conservative choice for the SD might then be 1.9, as per the speech subscale. Note that there was a significant change from ore to post in all outcomes.

**HUI sample size calculations:**

Interest is in the difference in change between the 5 age groups of interest. We can look for differences in change between age groups using a one-way analysis of variance where the omnibus test will show if there is a significant difference between any pair of groups.

We use a 5% significance level, power of 80%, and assume a SD=0.22 (from UKCISG) within each group and use the data from UKCISG change in means for each age group (where 0.23 is used for the youngest age group). So, the biggest difference between any pair of groups here is 0.07 units. With these specifications, a sample size of 995 would be required to find a significant difference between at least one pair of age groups.

If the largest difference between the oldest and youngest group was 0.1 with 0.025 difference between all adjacent groups, then a sample size of 470 would be needed to find a significant difference between at least one pair of age groups.

**SSQ sample size calculations:**

We have no data on the mean and SD for each age group but, using a 5% significance level and power of 80%, and assuming a SD=1.9 if the difference between the oldest and youngest age group is 2 units and there is a 0.5 difference between adjacent groups (so that the youngest group has the MCID in change but the oldest group makes no gain [note that this is not realistic since we know all ages gain]) then a sample size of 95 would be needed to find a significant difference between at least one pair of age groups.

The true difference between age groups is likely to be much smaller. Suppose the youngest age group gains 3 SSQ units for the speech subscale but the oldest age group gains only 2

units. Assume adjacent groups differ by 0.25. Then a sample of 350 participants would be needed to find a significant difference between at least one pair of age groups.

Repeated measures methods, which will be used to analyse the data are more efficient and so it is likely that smaller sample sizes will be needed than stated in the above calculations.

## 1.3.2 Analyses

### 1.3.2.1 Pass/Fail Criteria

Not applicable.

### 1.3.2.2 Primary Hypothesis and Analysis

The effectiveness of cochlear implantation may vary by adult age group. Effectiveness is defined by the gain in total SSQ or HUI3 scores. As the outcome is likely neutral with respect to implications the hypotheses are presented to look for significant differences rather than to prove equivalence: We are neither worried that older subjects receive less benefit than younger patients, or vice versa since overall benefit is already known for these. However, differences in the benefits may imply revision of rehabilitation and/or counselling for prospective candidates. Thus:

H0: There is no interaction effect between age group and visit on SSQ/HUI3 scores.

H1: There is an interaction effect between age group and visit on SSQ/HUI3 scores.

The proposed method of analysis is to use linear mixed-effects models (LMM). This allows determination of main (fixed) effects (visit, age group) and interaction effects, such as to answer the main objective while utilising all available data and controlling for repeated measures on the same individuals via a random effect for individual.

Tukey pairwise differences will be used to examine differences between age groups (if there is no evidence of an interaction effect) after adjusting for time if there is a significant main effect of age group. If an interaction effect is evident then differences between age groups at each time point can be estimated while controlling appropriately for pairwise testing.

The LMM approach allows the possibility of observing the influence of any continuous or categorical covariates of interest.

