13.6	Study Documents Online and Study Records	19
13.7	Data Management	20
14	Reporting of Results	20
14.1	Investigator.....	20
14.2	Sponsor.....	21
15	Withdrawal of Sponsor	21
16	Overview of Case Report Forms and Questionnaires available online	21

1 Registry Synopsis

Device(s):	All Cochlear devices, eligible for market release.
Study title:	Cochlear - Implanted Recipient Observational Study (Cochlear - IROS).
Participating sites:	Sites selected for voluntary participation in the observational study (Cochlear - IROS), using any Cochlear devices that are eligible for market release.
Study Duration per subject:	Two years follow-up from Baseline registration. Baseline registration online occurs just after the patient is implanted and prior to the first switch-on. Follow-up at 1 and 2 years is recommended to occur in parallel to routine Clinical evaluations. Evaluation at third year post implant follow-up is optional.
Start date	Dec 2011, with ongoing roll out to clinics and countries as languages become available for use. Review of study progress at regular annual intervals.
Number of subjects:	A minimum of 50 recipients per device. Several hundred subjects across device user groups and device configurations are aimed for enrolment in the study /registry.
Study/Registry Design:	
Prospective, longitudinal comparative repeated measures of benefits for implanted hearing impaired subjects, acting as their own intra-subject control, using a selection of subjective evaluation tools provided via an electronic platform for data entry and data collation within a secured environment. Longitudinal repeated evaluations commencing at Baseline (post-implant, pre-switch-on) and repeated annually for up to 3 years post implant.
 
Patient benefits will be compared to safety records for Cochlear devices eligible for market release gathered through post market surveillance. Inter-subgroup (to be classified by device use and configuration) comparisons of performance per assessment tool per interval shall be performed pending numbers of relative data sets.
 
Note: The registry platform is designed to support and sustain uniform data collection on unlimited number of prospectively implanted patients long term.

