Evaluation Materials	
Evaluation Tools comprising main measures for study endpoints made available electronically include:
 
 ○ Subjective self- assessment scales (clinically standardised: SSQ and HUI Mk III); ○ Patient profile forms (clinician and recipient questionnaire versions); ○ Hearing threshold measures (routine measures performed at the clinic) ○ Product specific evaluations as required
Inclusion criteria:	
 ○ Post-lingually deafened adults and adolescents who are newly implanted AND prior to first switch-on of their external device. ○ Unilateral, bilateral simultaneous recipients of any implant device(s) available with market approval from the company Cochlear®. ○ Children 10 years or older, and in accordance with local regulations and product labelling. ○ Mentally capable to respond to self-administered assessment scales ○ Willingness to participate and sign the Patient Informed Consent (PIC) form directly or signed by the legal representative. 
NOTE: Unilateral implant-users registered at baseline, electing to opt for a second sequential implant during the course of the 3 year follow-up period shall be re-classified accordingly there-after as sequentially bilaterally implanted.

Exclusion Criteria	
 Individuals excluded from participation in a registry according to national or local regulations. 							
Primary Objectives:	To evaluate longitudinal subjective benefit data using validated standardised questionnaires (HUI Mk3 and SSQ) for prospectively implanted adult and adolescent recipients compared to the preimplant condition. To assess daily use and issues reported through Cochlear's complaints and issues handling procedure.							
Secondary Objectives:	
To provide statistically valid data to support patient management decisions at the clinical, administrative, reimbursement and regulatory levels locally, nationally and internationally.
 
To establish benefits and device functionality for bilateral use over unilateral use for scientific, regulatory and market-oriented communications.
							
Evaluation Plan	Evaluations are performed at the Baseline interval (post-implant and pre-switch-on) with annual follow-up at 1 year, 2 years (and optionally at 3 years) post-implant. Clinicians and recipients are strongly encouraged to use all evaluation tools below.							
			Test interval	Baseline	Follow-up			Comments

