The Speech, Spatial and Qualities of Hearing Scale (SSQ), a hearing-disease questionnaire. Established as a sensitive measure to demonstrate benefits of bilateral versus unilateral hearing ability in the a variety of daily situations and a range of hearing abilities as the title suggests. (e.g. Noble, Tyler et al. 2008) . Cross cultural version translations are validated. This questionnaire version has been assessed for self-assessment via self-administration from the age of 9 years. This questionnaire is designed and validated to be administered for prospective assessment of hearing ability.

The Health Utilities Index - Mark III (HUI3), a generic health status and health-related quality of life questionnaire. Established as a sensitive measure to demonstrate impact of medical treatments over time in 8 areas, (vision, hearing, speech, ambulation, dexterity, emotion, cognition and pain). Normative data is available. Evidence of its effectiveness as a useful tool to compare and demonstrate superiority of bilateral CI vs unilateral CI vs baseline pre-implanted status has been published to date (e.g. Bichey et al. 2008). It should be noted that strictly speaking this questionnaire is designed and validated for prospective assessment. Cross cultural validated versions have been licensed and made available for use in this study. This questionnaire version has been assessed for self assessment via self administration by individuals 6 years of age and older.

Implant recipient questionnaire, a non-standardised questionnaire (**2 versions: Baseline and Post implant evaluation**) designed to gather basic patient hearing history, degree of residual hearing pre and post-operatively, implant models and serial numbers, additional demographics and vocational aspects for each individual.

6.1.3 Evaluation forms for completion by the Clinician:

The clinician is trained on data entry procedures for Cochlear-IROS by Cochlear following agreement to participate voluntarily in the registry. Data entry is to be performed by the clinician directly or other staff member via direct on-line electronic data entry with access provided through use of their password on any suitable computer within the clinic during or coinciding with the timing for routine annual clinic visits occurring after one, two and three years (optional) post implant for the patient in question.

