## 1 REAL LIFE OUTCOMES VERSUS AGE FOR CI

### 1.1 Overall objectives

- Clinical Evidence Strategy: Healthy Aging
- Pivotal Hypothesis: Are there differences in outcomes with CI for different age ranges, and impact on subject's life
- Primary measures: HUI3, SSQ (complete scales)
- Secondary measures: Changes in HUI3 >0.03, changes in SSQ >2 (i.e. dichotomisation of outcomes), changes in employment status pre and post (1 year, and sustained at 2 years), Medical leave after surgery, employment and other specific questions and listening effort (e.g. from SSQ).
- Age groupings for comparisons:
  - Use ABS-type age groupings 18-34, 35-44, 45-54, 55-64, 65+
  - Note that the younger age groups were combined due to sample size.
- Descriptive statistics of sub populations/ predictors (to be compared: pre and post, pre vs post, by age group, and as potential predictors in regression analyses)
  - Onset of deafness
  - Etiology
  - Hearing loss degree
  - HA use/presence (in the implanted ear at baseline and contralateral ear at baseline and visit 1)
  - Telephone use
  - Presence of tinnitus
  - Presence of dizziness
  - Employment status
  - Whether hearing ability negatively affected work
  - Has ability to do job changed post implant
  - Medical leave (taken and amount)
- Considerations:
  - Bilateral implant summaries were also of interest but were not possible due to small numbers.
  - Some of the above summaries may not be possible due to (subgroup) sample sizes.
  - The questions around employment and leave may not have been captured in a usable form, as such these variables will be explored more carefully, and analyses should be interpreted cautiously.

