**4.1.2.3 Secondary Hypotheses**

One factor which might influence HUI3 gain is the baseline HUI3 score. However, much of the HUI3 multi attribute score variation in this population is produced by the 6-point Hearing attribute (figure below – all CI subjects pre and post scores). This allows us to avoid comparing baseline and gain directly in HUI3 scores (partially correlated).

The hearing attribute can be divided into two broad classifications:  $\leq 3$  (0.71-1 in the figure), where all three indicate that the subject can understand what is said in a group conversation with at least three other people, with or without using a hearing aid, and  $>3$  (0-0.48), the converse, including not hearing at all either one-on-one or with three other people.

Table 2. Numbers of patients in HUI3 Hearing attribute categories 1-6; baseline rows, at visit 1 columns.

Value	6	5	4	3	2	1	Status classification
6	4	7	0	22	2	2	No hearing
5	4	9	1	31	1	1	Group No/with HA
4	0	0	0	2	0	0	Group No/with HA
3	2	3	0	32	1	2	Group OK/with HA
2	0	1	0	1	0	0	Group OK/with HA
1	0	0	1	3	0	1	Group OK/No HA

The baseline hearing attribute classification may be correlated with demographic characteristics and thus it is worthwhile to test this, as well as the influence of baseline hearing attribute on gain in multi-attribute score.

We see that 32 subjects are in category 3 both at baseline and at visit 1. The SSQ scores can be used to evaluate with more precision whether this group benefitted from cochlear implantation. Also the HUI3 multi-attribute score may indicate some change.

Thirdly, to look at the outcome questions in IROS such as whether an improvement in hearing was noted by patients.

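### SAP 1.3.2.2 reads an age-by-visit interaction on total HUI3 as a difference in implant effectiveness, but age differences in the course of non-hearing health would produce the same interaction

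*SAP*

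**What the plan says.** SAP 1.3.2.2 sets out to learn whether the effectiveness of cochlear implantation depends on age group. It gives the definition "Effectiveness is defined by the gain in total SSQ or HUI3 scores" and the alternative hypothesis "There is an interaction effect between age group and visit on SSQ/HUI3 scores". SAP 1.1 names HUI3 and SSQ as primary measures in full-scale form. The Protocol, under the self-assessment tools in section 6.1.2, lists the HUI3 areas as "vision, hearing, speech, ambulation, dexterity, emotion, cognition and pain".

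Only implanted recipients are enrolled, and the Registry Synopsis describes them as "acting as their own intra-subject control". SAP 1.3.3.1 expects data to two or possibly three years. SAP 1.3.2.2 permits covariates but prespecifies none for general health, and the predictors listed in SAP 1.1 include no measure of vision, mobility, cognition or pain.

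Section 1 of the SAP plans no analysis of the HUI3 hearing attribute. Section 4.1.2.3, for a different publication, does use it, tabulates it before and after implantation, and remarks that "much of the HUI3 multi attribute score variation in this population is produced by the 6-point Hearing attribute".

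**The concern.** The question is about the implant, whereas the test is about change in a generic health-utility total. Each recipient's own baseline removes stable differences in health between age groups: a constant difference goes into the age main effect and leaves the interaction alone. It does not remove differences in how health changes over follow-up. Without unimplanted people, external age norms or a separate look at the hearing attribute, the interaction combines two things: age differences in what the implant does, and age differences in the course of vision, ambulation, pain and the other areas.

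SAP 1.3.2.2 says that a difference may lead to changes in how candidates are rehabilitated or counselled. A significant HUI3 interaction could therefore be taken to mean that older recipients gain less from the implant when their hearing gain is the same. Because effectiveness is defined through SSQ or HUI3, and no rule covers disagreement between them, the HUI3 result can carry that conclusion alone.

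**Working it through.** **Inputs from the documents.** Five age groups (SAP 1.1); 5% omnibus test, SD of change 0.22, planning totals 995 and 470 (SAP 1.3.1); smallest important HUI3 change 0.03 (SAP 1.3.1); registry paired result t = 5.9659, df = 132, mean change 0.1490534 (SAP 4.1.2.1).

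**Assumptions.** Equal group sizes, which the SAP does not state but which reproduce its figures. Equal hearing gain at every age. An extra non-hearing decline *d*, from youngest to oldest, linear across the groups. The documents give no age-specific rate of non-hearing change, so a range of *d* is shown.

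**Method.** With a baseline and one follow-up visit and complete data, the age-by-visit test is the one-way ANOVA on change that the SAP uses for planning. Its noncentrality is λ = (N/5) × Σ(mean_i − grand mean)² / SD², with 4 and N − 5 degrees of freedom. Further visits or missing data would alter the figures somewhat.

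**Reproducing the plan.**
- Mean gains 0.23, 0.21, 0.16, 0.20, 0.18 have grand mean 0.196 and sum of squares 0.00292. At N=995, λ = 199 × 0.00292 / 0.0484 = 12.01 and power is 80.0%.
- A linear gap of 0.1 has sum of squares 0.00625. At N=470, λ = 94 × 0.00625 / 0.0484 = 12.14 and power is 80.3%.

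Both planning totals reproduce.

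**SD from the registry.** Standard error = 0.1490534 / 5.9659 = 0.02498; SD = 0.02498 × √133 = 0.288. This is not split by age group.

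**Equal hearing gain, non-hearing gap *d*.** For a linear gap the sum of squares is 0.625*d*², so λ = 0.125 × N × *d*² / SD². For *d* = 0.03, N=995 and SD 0.22, λ = 0.125 × 995 × 0.0009 / 0.0484 = 2.31, and the test rejects 19% of the time.

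| *d* | N=470, SD 0.22 | N=995, SD 0.22 | N=470, SD 0.288 | N=995, SD 0.288 |
|---|---|---|---|---|
| 0 | 5% | 5% | 5% | 5% |
| 0.01 | 5.6% | 6.3% | 5.3% | 5.7% |
| 0.02 | 7.5% | 11% | 6.4% | 8.2% |
| 0.03 | 11% | 19% | 8.4% | 13% |
| 0.04 | 17% | 33% | 11% | 20% |

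A simulation (4,000 runs per setting, SD 0.22 split into an assumed hearing part of 0.18 and an independent remainder) agreed with the SD 0.22 columns at the gaps common to both, 0 and 0.03. In it, the same test on the hearing part alone rejected 4.5% to 5.2% of the time for gaps from 0 to 0.10.

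**The hearing attribute as a supportive outcome.** In SAP 4.1.2.3, Table 2, the number at level 3 at visit 1 is 22 + 31 + 2 + 32 + 1 + 3 = 91 of 133, and 32 of these were at level 3 at baseline too. Change in the attribute therefore depends heavily on where a patient started.

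**The case against.** The strongest reply is that total HUI3 is a proper outcome here. SAP 1.1 asks about impact on the recipient's life as well as outcomes by age, and the hypotheses concern scores. If total gain differs by age, rejection is correct. That stands: a reader might infer an inflated type I error from the table, but the percentages are correct rejections of the literal null. What they measure is how often a result could be credited wrongly to the implant.

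Second, SSQ is hearing-specific, is also primary and goes through the same model, and section 4 says hearing drives much of the HUI3 variation. Both points soften the concern. Neither removes it: the section 4 remark carries no figure and concerns overall variation, not age differences in change, and no rule links the SSQ and HUI3 results.

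Third, the declines are assumed, and at 0.01 to 0.02 the excess over 5% is small. That also stands.

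Two stronger readings are tempting. One is that poor health in other areas shrinks the total-score gain from a given hearing gain and so biases the test. The documents give no HUI3 scoring function to support this, and such shrinkage would be a real difference in total utility gain, which is the outcome the SAP defines and which no untreated group would remove. The other is that the age pattern in the published UK cohort could be ageing alone. Its mean gains (0.24, 0.22, 0.21, 0.16, 0.20, 0.18) do not fall steadily with age, its oldest-to-youngest gap of 0.06 exceeds every decline considered here, and the documents say nothing about non-hearing change in that cohort.

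**Conclusion.** The concern holds as one of interpretation. Section 1 attributes an age-by-visit interaction on an eight-area total to the implant, with nothing planned to separate hearing from other health. The sample-size figures and the test of the literal null are sound.

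The size depends on the assumed decline, the SD and N. The excess over 5% is slight for a gap of 0.01 under either SD. At a gap equal to the SAP's own 0.03 threshold, rejection is 8.4% to 11% at N=470 and 13% to 19% at N=995. Both totals are planning requirements, not numbers achieved. The results also rest on equal groups, a linear age gradient and a single follow-up visit.

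**What to change.** Keep total HUI3 as a primary measure. In SAP 1.3.2.2:

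- Add the same age-by-visit model on the HUI3 hearing-attribute utility as a supportive analysis, read together with the SSQ result, and show baseline hearing level by age group.
- State that an interaction on total HUI3 without a similar pattern in SSQ or the hearing attribute will be reported as an age difference in overall health-utility change, and is not by itself evidence that the implant works less well at some ages.
- Optionally, describe by age group the change in the areas least likely to respond to the implant (vision, ambulation, dexterity, pain). Do not treat the non-hearing areas as a formal negative control: nothing in the documents says that speech, emotion and cognition are unaffected by an implant.

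The cost is some wording and one extra model on data already held. The drawback is a coarse six-level attribute that clusters at level 3 after implantation, which is why it should support the interpretation and not decide it.

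### The mixed model for age group by visit rests on a random effect per individual, with no stated covariance and no safeguard if variances or correlations differ between visits

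*SAP*

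**What the plan says.** The primary null hypothesis in SAP section 1.3.2.2 is: "There is no interaction effect between age group and visit on SSQ/HUI3 scores". The proposed method is a linear mixed model with visit, age group and their interaction as fixed effects. It controls for repeated measures "via a random effect for individual". The follow-up step is: "If an interaction effect is evident then differences between age groups at each time point can be estimated". No residual covariance, visit-specific variance, random slope, robust standard error, degrees-of-freedom method or sensitivity analysis is named.

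Section 1.3.3.1 expects data up to 2 or possibly 3 years. With baseline, three or four visits can therefore enter the model, in line with the schedule in Protocol section 6.1.1.

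The only variance data for the two scales at separate visits are in Table 2 of section 1.3.1. They cover one pre-implant and one post-implant measurement in a small sample, not split by age.

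**The concern.** A random intercept fixes the covariance pattern in advance. Baseline describes the pre-implant condition, while years 1 and 2 are both reported with the implant in use. Two post-implant scores could well correlate more strongly with each other than with baseline, and the spread of scores could change after implantation. If so, a random-intercept model averages unlike quantities and its standard errors are wrong for particular comparisons.

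At stake are the error rate of the primary interaction test and the precision claimed for the age-group differences that follow it.

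**Working it through.** **1. The plan's own figures.** The sample sizes use a one-way ANOVA on change. "We use a 5% significance level, power of 80%, and assume a SD=0.22 (from UKCISG) within each group" gives the inputs, with five equal age groups. The noncentrality is λ = n·Σ(mᵢ − m̄)²/SD². For mean changes 0.23, 0.21, 0.16, 0.20, 0.18, Σ(mᵢ − m̄)² = 0.00292. With n = 199 per group, λ = 199 × 0.00292/0.0484 = 12.0, which gives 80% power at N = 995. The other three figures (470, 95, 350) also reproduce. These calculations use a single change score, so they say nothing about covariance over three visits.

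**2. Pre-post correlation implied by Table 2.** The SD rows are "SD 0.188 0.168 0.182 1.907 2.104 1.356" (HUI3 pre, post, difference; then Spatial) and "SD 1.707 1.685 1.919 1.355 1.726 1.289" (Speech; then Qualities). With r = (s₀² + s₁² − s_d²)/(2·s₀·s₁):

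- HUI3: (0.03534 + 0.02822 − 0.03312)/0.06317 = 0.48
- Spatial: (3.637 + 4.427 − 1.839)/8.025 = 0.78
- Speech: (2.914 + 2.839 − 3.683)/5.753 = 0.36
- Qualities: (1.836 + 2.979 − 1.662)/4.677 = 0.67

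These are approximate, because the pre, post and paired sample sizes differ (29, 38 and 27 for HUI3).

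**3. Equal variances.** Post/pre SD ratios, with the Pitman-Morgan p-value: HUI3 0.89 (0.53), Spatial 1.10 (0.36), Speech 0.99 (0.93), Qualities 1.27 (0.048, unadjusted for four tests). The 6-level Hearing attribute table in SAP section 4.1.2.3 gives SDs of 1.40 at baseline and 1.16 at visit 1 (p = 0.027), but that is one component of HUI3.

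**4. Two visits, complete data.** The model variance of a change is the mean of all pairwise difference variances. With two visits there is only one pair, so it equals s_d². The change test is exact (5.0%), whatever the variances.

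**5. Three visits, complete data.** Assumptions: the year-2 SD equals the year-1 SD, the baseline-to-year-2 correlation equals baseline-to-year-1, and r₁₂ (year 1 to year 2) is 0.7, 0.8 or 0.9. The documents give none of these.

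HUI3 with r₁₂ = 0.8:
- True variance of change from baseline: 0.182² = 0.03312.
- Year 1 to year 2: 2 × 0.168² × 0.2 = 0.01129.
- Model value: D = (2 × 0.03312 + 0.01129)/3 = 0.02585.
- Baseline-to-year-1 SE ratio: √(0.02585/0.03312) = 0.883, so type I error is 2[1 − Φ(1.96 × 0.883)] = 8.3%.

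For the interaction test, the true contrast variances are 0.01129/2 = 0.0056 and 0.02585 − 0.0056 = 0.0202, where the model assumes they are equal. Weighted chi-squares with 8 and 390 degrees of freedom (5 groups of 40, an illustrative size; 400,000 draws) give 7.0%.

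Type I error (%) for r₁₂ = 0.7 / 0.8 / 0.9:

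| Outcome | Interaction | Baseline to year 1 | Year 1 to year 2 |
|---|---|---|---|
| HUI3 | 5.9 / 7.0 / 8.4 | 7.3 / 8.3 / 9.5 | 1.2 / 0.3 / <0.1 |
| Speech | 6.3 / 7.2 / 8.5 | 7.6 / 8.6 / 9.7 | 0.9 / 0.2 / <0.1 |
| Spatial | 5.5 / 5.0 / 6.1 | 3.6 / 5.1 / 7.5 | 8.1 / 4.7 / 1.0 |
| Qualities | 5.0 / 5.3 / 6.9 | 4.7 / 6.2 / 8.2 | 5.6 / 2.8 / 0.4 |

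Direct simulation for HUI3 gave 6.2, 6.7 and 8.4% for the interaction. If r₁₂ equals the pre-post value of 0.48, the HUI3 interaction test is at 5.0%. With loss of 27% per year (117 of 161 retained at 1 year, the centre in SAP section 4.1.1), the HUI3 baseline-to-year-1 error is 5.7% to 8.0% for r₁₂ from 0.6 to 0.9.

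**6. Age groups compared at one visit (two visits, complete data).** The model uses the average variance (s₀² + s₁²)/2.
- HUI3: 0.03178. SE ratios are √(0.03178/0.03534) = 0.948 at baseline and √(0.03178/0.02822) = 1.061 post-implant. Type I error is 6.3% and 3.8%.
- Qualities: 2.408. SE ratios are 1.145 and 0.899. Type I error is 2.5% and 7.8%.

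**The case against.** A reader might infer that the SAP's own data contradict the random-intercept assumption. They do not. With one pre-post pair per outcome, equality of correlations across visit pairs cannot be tested. The four values in step 2 differ between outcomes, not between visit pairs. The SAP's remark "For SSQ the SD for change varies between 1.3 and 1.9" likewise compares subscales. Equal variance is not rejected for HUI3, Spatial or Speech. Qualities is borderline and is a subscale, whereas the SSQ primary outcome is the total score, for which no SDs are given.

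Nor do the documents support saying that change contrasts are always anti-conservative. For Spatial with r₁₂ = 0.7 the direction reverses: 3.6% for baseline to year 1 and 8.1% for year 1 to year 2. The largest errors in the table also belong to change contrasts that section 1.3.2.2 does not name; it plans comparisons within each visit.

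It is also fair to say that the SAP's phrase is brief and excludes no richer structure, that no pass/fail decision depends on the test (section 1.3.2.1), and that the implied correlations are unstable. The SD of HUI3 change is 0.182 in Table 2, 0.22 in the sample-size section, and 0.288 from the paired t-test in section 4.1.2.1 (0.14905/5.9659 × √133).

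All of this limits the claim. It does not remove the gap: the default reading is a restrictive model, three or four visits are expected, and nothing protects the inference if the restriction fails. An unknown correlation is a reason to estimate it.

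**Conclusion.** The point holds as a gap in specification with a conditional effect. Under the assumptions of step 5, the HUI3 interaction test runs at about 6% to 8% instead of 5%, and at about 5% to 7% for Spatial and Qualities. The planned comparisons at each visit can err in either direction if variances differ by visit. The effect on total SSQ cannot be calculated from the documents. The inflation is modest, but it falls on the primary hypothesis. Stating the covariance in advance matters more here because the SAP's Introduction says that deviations from the plan need not be reported.

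**What to change.** In SAP section 1.3.2.2, make the primary mixed model one with an unstructured within-subject covariance (visit-specific variances and correlations) and Kenward-Roger or Satterthwaite degrees of freedom. State the fallback order if it does not converge: first a heterogeneous structured covariance such as heterogeneous Toeplitz, then a random intercept with cluster-robust standard errors.

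The cost is a few lines of text and no new data; the methods are available in R. An unstructured covariance has 6 parameters for three visits or 10 for four, against 2 for a random intercept. It may fail to converge where later visits are sparse, which the fallback order covers.
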